Aerobes	Fresh	2.53E+05	1.76E+05
	1 freeze-thaw	4.30E+05	4.43E+05
Anaerobes	Fresh	5.80E+07	3.96E+07
	1 freeze-thaw	6.20E+07	5.29E+06

CFUs per mL of Capsules G3 Microbial Emulsion Matrix

_CFUs per mL of stool homogenized 1:1 (w/v) with buffer containing 12.5% glycerol and 0.9% saline, after one freeze-thaw cycle

	per mL
Aerobes	4.53E+06
Anaerobes	1.47E+09
Spores	2.00E+06

These concentrations will be used for the upcoming trial to ensure that the material concentrations in our older trials are expanded.

- We anticipate providing 5 capsules at a time for the oral FMT and 60ml of the FMT enema.
- The placebo for the oral FMT will be made using identical capsules as the active drug, except it will contain 10%/weight trehalose (the cryoprotectant used in preparation of freeze-dried microbiota) and the rest carboxymethylcellulose. Since the capsules are not transparent and have no specific smell or taste, there should be no difficulty in maintaining double blinding.
- The placebo for the liquid formulation is non-bacteriostatic, sterile phosphate buffered saline containing 10% USP grade glycerol. Each dose will be packaged in individual cryobags, just as the active drug.

Study Design

Overall objective: To determine the effect of dual oral and rectal administration of FMT from a rational donor on clinical outcomes (hospitalizations, brain function, quality of life) and host-microbiota interactions (microbial composition and bile acid composition with systemic and intestinal inflammation), compared to single route of administration and placebo, along with a second oral capsular FMT vs placebo administration in patients with cirrhosis and HE using a randomized, phase II clinical trial.

Design overview:

Four groups of outpatients with cirrhosis will be randomized using random sequence generator into placebo and FMT groups and followed for 6 months under an FDA IND double-blind clinical trial.

Group 1: Dual oral and rectal FMT, Group 2: Oral FMT and rectal placebo, Group 3: Oral placebo and rectal FMT and Group 4: Oral and rectal placebo

A repeat oral capsular FMT vs placebo based on the group assignments above will be provided to every subject in at day 30.

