None of the Veterans included in this study will have any visits at VCU. Non-Veterans will be recruited according the approved VCU protocol and will sign the VCU consent. These potential participants will also be shown the approved VA Consent form in order to provide them the full scope of the study. These non-Veterans will have a choice to perform all subsequent studies at VAMC or only the 2 treatment visits, which are visits 2 and 4. When they first arrive at the VAMC for their in-person visits, they will be asked to sign the VA IRB approved consent form before proceeding. Neither of the treatment visits will be performed at VCU even if the enrollee is a non-Veteran.

[name], who is the PI at both sites, will ensure that subjects meet criteria for enrollment and reporting to both IRBs as necessary. An MOU will be signed.

Safety and hospitalization analysis:

Using detailed FDA-approved protocols, patients will be adjudged based on adverse events and serious adverse events at every visit and during the 6-month follow-up. Any SAEs or deaths in an FMT-randomized group will require the DMC to define the "relatedness" of the event to the FMT. If the DMC votes that this is related to the FMT, then this will be sent to the FDA, and Molecular and Cellular Therapeutics (GMP) facility at the University of Minnesota to invoke stopping rules as detailed below. The safety endpoints will be all-cause hospitalizations, defined as unplanned, non-elective hospitalizations within the 6-month period. The reason for the hospitalization will be analyzed by the investigating team and divided into liver-related, liver-unrelated, planned or elective. The latter two categories will not count towards the study but the first two will be analyzed by the team and submitted to the DMC. Other SAEs will be analyzed per FDA definitions. AEs that do not meet the standards of SAE will be evaluated at each visit and be compiled to define trends in one group compared to the other.

Reasonably foreseeable significant risks:

Physical risks:

- 1. Infection or bruising during blood draw
- 2. Procedure-related adverse events from enema (e.g. perforation, bleeding etc)
- 3. Pill-associated dysphagia
- 4. FMT material-related adverse events (e.g. transmissible infection, allergic reaction)

Psychological/Social risks:

(b) Very small risk of loss of confidentiality and privacy

Specific issues to be captured will be

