1. Study procedure-related adverse events from enema (e.g. perforation, bleeding, etc.)

- 2. FMT material-related adverse events (e.g. transmissible infection, allergic reaction)
- 3. Capsule ingestion-related adverse events (pill-associated dysphagia)

4. Short-term safety: Both solicited and unsolicited adverse events will be recorded by, clinical assessment at all in-person visits. The subjects will have the ability to telephone the study team at any point during the study.

5. Long-term safety: follow-up monthly till 6 months to evaluate for SAEs (listed below).

Solicited AEs throughout the trial will be

- (a) fever:
- (b) diarrhea
- (c) vomiting
- (d) constipation
- (e) GI bleeding
- (f) abdominal cramping and pain
- (g) Development of HE (confusion/altered mental status):
- (h) Development of infections, specifically spontaneous bacterial peritonitis
- (i) New onset or significant worsening of chronic medical conditions
- (j) New potentially transmitted infections

We do not expect the infections to occur at a higher rate than the natural history of cirrhosis at this stage. This is borne out by our enema study, in which the FMT group had no infections. Also, a nasojejunal study performed by Phillip et al in severe alcoholic hepatitis, whose MELD scores were much higher than our proposed patients, did not reveal a poor safety profile. We will monitor for all infections and specifically for spontaneous bacterial peritonitis (SBP).

All safety assessments in FMT will be compared to placebo groups given the advanced nature of the cirrhosis and the association of several of these symptoms in the natural history of the disease

Stop-points or reportable adverse events

Any hospitalization or event that is life-threatening will be deemed a serious adverse event in the FMT group and reported to the IRB, FDA, DMC and Molecular and Cellular Therapeutics (GMP) facility at the University of Minnesota within 72 hours (per usual protocol).

This will include the development of an infection that is gut-based/not gut-based:

Gut-Related

- Spontaneous Bacterial peritonitis
- Infectious diarrheal illnesses

Others

- UTI
- Respiratory
- Skin/soft-tissue
- Bacteremia

Overall Study Halting Rules

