Specific safety findings will result in temporarily suspending enrollment until a safety review is convened, the objective of which is to determine whether the study should continue per protocol, proceed with caution, be further investigated, be discontinued, or be modified and then proceed. Suspension of enrollment is another potential outcome of a safety review. This will be done if the assigned infection is in the FMT group since this patient population is prone to infections.

Subsequent review of serious, unexpected, and related AEs by the Data and Safety Monitoring Board, IRB, the PI, or the FDA or relevant local regulatory authorities may also result in suspension of further trial interventions/administration of FMT at a site. The FDA and PI retain the authority to suspend additional enrollment and study interventions/administration of FMT for the entire study, as applicable. The PI and the adjudication panel will make the initial decision. The subsequent safety review by the IRB and FDA will then decide if the study can resume.

Findings that will trigger a safety review are

Findings that will trigger a safety review are

- o Death related to FMT material or study procedures in any subject;
- New potentially transmitted infection in five or more subjects assigned to FMT - i.e., cannot exdude transmission and/or attribution is

pending investigation/Data Monitoring Committee (DMC) adjudication;

- Any single potential transmitted infection assessed as possibly, probably, or definitely related to FMT by the investigator and DMC.
- One or more subjects assigned to FMT has a serious, unexpected AE assessed as possibly, probably, or definitely related to FMT by the investigator and DMC; Five or more subjects (per assigned group) develop a new diagnosis of a medical condition or immune-mediated disease considered probably, or definitely related to FMT.
- Five or more severe AEs of a similar nature occurring in different subjects and assessed as definite, possible or probable relatedness to study product in groups assigned to FMT (per assigned group)

FDA/CBER will be notified by phone or fax within 72 hours if the study is halted for review.

Individual study halting rules

- (1) patient's choice
- (2) change in GI adverse events with a magnitude of 3 increase over baseline
- (3) fever and signs of infection (including WBC count >12,000/ml)
- (4) SAE development including cirrhosis complications (OHE) and hospitalizations for

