- any cause including bleeding, nausea, vomiting, or other GI conditions
- (5) increase in MELD score by 8 or more
- (6) Increase in AST, ALT or Alkaline phosphatase to 10X ULN
- (7) Non-elective Hospitalization

Even if the subject is withdrawn before 30 days, they will still be followed till 6 months for safety.

Health risks (please see adverse events table attached):

Adverse events will be both for the FMT material, placebo as well as for the procedures. These risks are listed in the Risk Section of the informed consent.

These possible adverse events will be:

- (a) Fever: yes or no answer with grading based on actual temperature on examination
- (b) diarrhea (will be asked to grade them from 0-4 compared to baseline)
- (c) abdominal cramping and pain (will be asked to grade them from 0-4 compared to baseline)
- (d) vomiting (will be asked to grade them from 0-4 compared to baseline)
- (e) Development of HE (Altered mental status) in every group: will be monitored by clinical examination through the West-Haven Criteria²⁵. We will be closely monitoring all subjects for this development, including a clinical examination by a gastroenterologist at every visit.

(f) Development of infections specifically spontaneous bacterial peritonitis -Fever will be reconfirmed by measuring by the study nurse and if it is confirmed, a detailed investigation into the cause of the fever will be performed as part of standard clinical care and the patient will be withdrawn from the study.

-Vomiting, constipation, GI bleeding, abdominal cramps and diarrhea: If the patient's diarrhea and abdominal cramps change in a magnitude of 3 over their baseline values per the AE chart (patients with cirrhosis often have these symptoms at baseline), they will be withdrawn from the study.

-Infections that occur in the FMT group will be thoroughly investigated according to standard clinical care to prove whether they were associated with the FMT.

Adverse Event Grading Chart

 Volunteer Study ID:
 Date:
 Time:

 Study Start Date:
 Current Visit number:

*Volunteer's responses will be marked on grading sheet by circling the appropriate grade or indicating no symptoms.

PARAMETER COMPARED TO BASELINE	GRADE 1 MILD	GRADE 2 MODERATE	GRADE 3 SEVERE	GRADE 4 POTENTIALLY LIFE-THREATENING
ESTIMATING SEVERITY	(GRADE		•	•

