Dehydration	Increased oral fluids indicated; dry mucous membranes; diminished skin turgor	IV fluids indicated <24 hours	IV fluids indicated >24 hours	Life-threatening consequences (e.g. hemodynamic collapse)
Constipation	NA	Persistent constipation requiring regular use of dietary modifications, laxatives, or enemas	Obstipation with manual evacuation indicated	Life-threatening consequences (e.g., obstruction)
Procedural Enema	Rectal discomfort; minor bleeding <24 hours on toilet paper	Rectal discomfort; minor bleeding >24 hours on toilet paper	Gross hematochezia	Bowel perforation
Change in mental status (West-Haven Criteria)	No change in orientation and no asterixis	Disorientation to time, asterixis	Disorientation to place or person, asterixis, lethargy and stupor	Coma
MELD score increase (includes INR, bilirubin and creatinine)	<3	3-7	>8	NA
Serum WBC	NA	NA	>12,000/ml or <1000/ml	NA
AST	NA	≥ 5.0 to < 10.0 x ULN	≥ 10.0 x ULN	NA
ALT	NA	≥ 5.0 to < 10.0 x ULN	≥ 10.0 x ULN	NA
Alkaline phosphatase	NA	≥ 5.0 to < 10.0 x ULN	≥ 10.0 x ULN	NA

Specific investigation of the infection related to the FMT in those assigned to the FMT group:

- 1. Regular clinical care of the subject according to the infection developed will include the appropriate cultures and relevant antibiotics will be started
- 2. Stool tests from the patient will be compared to the donor safety sample when a CLIA-

certified assay is available

3. Contact will be made with the FMT suppliers to evaluate this batch of the donor. Specifically, the cross-referenced drug master file has the means to track down the lots and batches of the donors. In the event of a suspected adverse event related to the potential transmission of an infection, an immediate initial consultation will be held between the researchers and the Chief Medical Officer of Molecular and Cellular Therapeutics (GMP) facility at the University of Minnesota ([name]) to gather further information. This will be followed by a detailed collaborative investigation as follows:

The investigation will entail:

a. Strict donor material quarantining during the investigation

b. Rescreening of the donor safety aliquot and the donor for infectious diseases as well as risk factors for the suspected infectious disease

c. Consultation with external experts in infectious diseases and gastroenterology with extensive experience in FMT.

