d. Full Advisory board review at Molecular and Cellular Therapeutics (GMP) facility at the University of Minnesota to track the donors

Laboratory:

Lab values for WBC counts, serum AST, ALT, Alkaline phosphatase, serum bilirubin, INR and serum creatinine (all three are in MELD score) will be followed.

These criteria will be graded per the chart as well.

The lab values that will be followed from an adverse event perspective will be:

- WBC count: a new >12,000/ml or <1000/ml in the presence of fever will necessitate investigation of an infectious source
- Worsening of the MELD score by 8 or higher will be considered significant
- Increase in AST, ALT and alkaline phosphatase >10 ULN will be considered significant although this change is not expected in cirrhotic subjects

[name] asks subjects to allow him to keep a portion of their blood, urine and stool specimens collected during the study to be used for future testing. Subjects agreeing to this will have a portion of their blood, urine and stool specimens stored in a research laboratory at the McGuire DVAMC. The samples will be de-identified. This means that no information that can identify a subject will appear on the samples. Subjects do not have to agree to this in order to participate in the study. If at any time during or after the study, a subject decides they want their samples destroyed, the subject can contact [name] at [contact] and request that their samples be destroyed.

Adverse Events Reporting

[name] will function as both the Investigator and the Sponsor during the conduct of this study. [name] will be responsible for reporting all safety observations (adverse events and serious adverse events) to the FDA

A. Definitions

1. Adverse Event (AE)

An AE is any untoward medical occurrence in a patient or study subject administered FMT due to the material or procedure that does not necessarily have a causal relationship with this treatment. An AE can therefore be any unfavorable and unintended sign (including an abnormal laboratory finding), symptom, or disease temporally associated with the use of a FMT, whether or not related to the FMT.

• AEs may be new events or may be pre-existing conditions that have become aggravated or have worsened in severity or frequency.

• AEs may be clinically significant changes from baseline in physical examination, laboratory tests, or other diagnostic investigation (e.g. laboratory results, radiographic findings).

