Pregnancy is not an AE; however, if a female subject becomes pregnant during the conduct of the study, the Investigator/Sponsor is responsible for notifying the FDA.

2. Serious Adverse Event (SAE)

A serious adverse event is any adverse experience occurring during or after FMT that results in any of the following outcomes:

Death

• Life-threatening experience

Note: An adverse event or suspected adverse reaction is considered "life-threatening" if, in the view of the Investigator/Sponsor, its occurrence places the patient or subject at immediate risk of death. It does not include an adverse event or suspected adverse reaction that, had it occurred in a more severe form, might have caused death.

• Requires inpatient hospitalization or prolongation of existing hospitalization *Note*: Adverse events requiring hospital admissions that are less than 24 hours in duration do not meet this criterion. A scheduled hospitalization for a pre-existing condition that has not worsened during participation in the study does not meet this criterion. Pre-planned hospitalizations for an elective medical/surgical procedure or routine check-ups do not meet this criterion.

• Results in persistent or significant disability or incapacity

- Results in a congenital anomaly or birth defect
- Results in an important medical event

Note: Important medical events are those that may not be immediately life threatening or result in death or hospitalization but may jeopardize the patient or may require intervention to prevent one of the outcomes listed in the definition above.

3. Planned Hospitalization

A hospitalization planned prior to intervention is to be considered a therapeutic intervention and not the result of a new SAE. If the hospitalization or procedure is executed as planned, it will be recorded in the subject's medical history or procedures. However, if the event/condition worsens during the study, it must be reported as an AE.

4. Adverse reaction

An adverse reaction means any adverse event caused by FMT or placebo. Adverse reactions are a subset of all suspected adverse events for which there is reason to conclude that FMT or placebo caused the event.

5. Suspected Adverse Reaction

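### Several safety rules apply only to FMT-assigned subjects, conflict with arm-neutral text, and cannot be followed without knowing allocation in a double-blind trial

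*Combined protocol and SAP*

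**What the plan says.** The Design overview has subjects "followed for 6 months under an FDA IND double-blind clinical trial", and the Visit 4 text keeps the blind through the second dose. Endpoints and Plan of Analysis makes FMT-related SAEs over six months, HE recurrence included, the primary endpoint. The safety text states that FMT will be compared with placebo on all safety assessments.

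These rules are conditional on FMT assignment:

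- The stop-points section has this rule: "Any hospitalization or event that is life-threatening will be deemed a serious adverse event in the FMT group and reported to the IRB, FDA, DMC". The manufacturing facility must be told too, all within 72 hours.
- Safety and hospitalization analysis: "Any SAEs or deaths in an FMT-randomized group will require the DMC to define the" relatedness of the event.
- Health risks: "Infections that occur in the FMT group will be thoroughly investigated according to standard clinical care to prove whether they were associated with the FMT".
- The infection-investigation section, headed for those assigned to FMT: "Stool tests from the patient will be compared to the donor safety sample when a CLIA" certified assay exists. Contact with the supplier follows.
- Overall Study Halting Rules, after the sentence on suspending enrolment: "This will be done if the assigned infection is in the FMT group since this patient population is prone to infections".

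Other text is not limited by arm. Safety and hospitalization analysis counts unplanned hospitalization from any cause. Health risks says adverse events cover placebo and that HE is monitored in every group. Assessment of Causality refers all SAEs to the panel. The reporting section puts every AE on the case report form.

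The definitions are mixed. The AE definition begins "An AE is any untoward medical occurrence in a patient or study subject administered FMT", and the SAE definition is timed from FMT. Its hospitalization criterion carries the note "Adverse events requiring hospital admissions that are less than 24 hours in duration do not meet this criterion", and it also excludes scheduled and elective admissions.

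**The concern.** A safety comparison with placebo needs the same event to be classified, adjudicated and reported in the same way whichever arm the subject is in. Here the primary endpoint depends on two classifications, serious and FMT-related, and for each of them at least one section ties the rule to FMT assignment while another does not. Staff would have to choose which section to follow, and two literal readings give different endpoint counts.

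The second issue is the blind. A rule that starts from whether the subject is in the FMT group can be applied only by someone who knows the answer. The subjects affected are those with events. If the person who learns the arm also judges causality, or takes part in later HE grading, cognitive testing or quality-of-life assessment, those judgements are no longer blinded for the subjects who contribute most to the endpoint.

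**Working it through.** **Inputs.** From the Sample size paragraph: 25 per group; alpha 0.05; six-month hospitalization of 80% under standard of care in the earlier enema trial; 30% assumed for rectal FMT alone, a similar rate for oral FMT alone, and 10% for the combination. No rate is stated for double placebo, so 80% is an assumption here.

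**The plan's own figure.** Take a four-group chi-square test with 3 degrees of freedom and rates 80/30/30/10%. The mean rate is (0.80 + 0.30 + 0.30 + 0.10)/4 = 0.375. The sum of squared deviations is 0.425² + 2 × 0.075² + 0.275² = 0.2675. The noncentrality is n × 0.2675/(0.375 × 0.625) = 1.141n, or 28.5, 22.8 and 17.1 for n = 25, 20 and 15. Power is 99.8%, 98.8% and 94.9%, against the stated 100%, 98% and 94%. This agreement suggests that the plan also used 80% for placebo. The sample size does not depend on the present point.

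**Subjects expected to be hospitalized.**

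- FMT arms: 25 × (0.10 + 0.30 + 0.30) = 17.5
- Placebo arm: 25 × 0.80 = 20
- Total: 37.5, so about 37 of 100

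If placebo subjects were admitted only at the 30% single-route rate, the total would be 17.5 + 25 × 0.30 = 25. The range is therefore about 25 to 37 subjects.

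**One unplanned admission of under 24 hours, read literally.**

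| Question | FMT arm | Placebo arm |
|---|---|---|
| SAE because of the admission? | Yes under Stop-points; no under the SAE definition | Stop-points is silent; no under the SAE definition |
| Reporting | IRB, FDA, DMC and supplier in 72 hours, related or not | If serious on another criterion and unrelated: local IRB in 5 days, FDA in the annual report |
| DMC relatedness vote, if an SAE | Required under Safety and hospitalization analysis | Not required there; Assessment of Causality refers all SAEs |
| Counted as a hospitalization? | Yes | Yes |

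Only the last row is the same in both arms.

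**Who would need allocation.** The sponsor-investigator is the only reporter named (Adverse Events Reporting) and also assesses causality, with help from the DMC. Under Overall Study Halting Rules, the PI shares the initial decision with the adjudication panel. The infection investigation opens with a consultation between the researchers and the supplier. The DMC meets three times a year, and no 72-hour route through it is described. The documents give no unblinding procedure and do not say whether the DMC sees allocation. They also do not define the FMT group, although three of the four arms receive some FMT.

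**The case against.** The strongest reply is that most counting text is arm-neutral and that the FMT-only phrases are loose drafting. All-cause hospitalization has no arm limit and no 24-hour threshold, and elective admissions are left out of it for everyone. All AEs are recorded. The protocol also uses FMT as a label for the intervention: Visit 4 speaks of placebo FMT, and an adverse reaction is defined for FMT or placebo. This stands in part. The text contradicts itself rather than setting one clear differential rule, and the hospitalization count is not affected.

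A reader might go further in several ways that the documents do not support:

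- **Placebo-arm events are not AEs.** The opening of the AE definition invites this, but Health risks says that adverse events cover placebo.
- **Related SAEs in placebo are zero by rule.** The FMT-only vote suggests it, but Assessment of Causality has the investigator assess every AE and refers all SAEs to the panel.
- **An overnight HE admission is an SAE only in the FMT arms.** That requires a stay under 24 hours. Even then, the important-medical-event criterion could apply, and the individual halting rules list overt HE under SAEs without naming an arm.
- **More work-up finds more infections under FMT.** Fever work-up and infection monitoring are arm-neutral. The FMT-only steps trace the source of an infection already found.
- **The blind must be broken at every event.** This is an inference. An investigational pharmacy dispenses and an independent DMC votes, so a blinded route is possible. IRB reports are also required for unrelated SAEs, so an IRB report alone need not reveal the arm.

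What remains is that the plan assigns nobody outside the site team to apply the arm-dependent rules, and that the sections disagree on seriousness and adjudication.

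**Conclusion.** The point holds as an internal conflict with consequences for the primary endpoint. Stop-points and the SAE definition disagree on short and elective admissions. The FMT-only relatedness vote disagrees with the referral of all SAEs. Followed literally, the placebo comparison of FMT-related SAEs is not like for like.

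The possible loss of blinding covers about 37 of 100 subjects. This figure assumes the plan's 80% standard-of-care rate for placebo and that allocation is checked at first admission. It counts subjects exposed to unblinding, not subjects whom the plan says will be unblinded.

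A reader might want to express the unequal counting as a spurious excess of SAEs under FMT in percentage points. The documents do not give the share of admissions under 24 hours, so no such figure can be supported.

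**What to change.** Amend the wording so that every randomised subject in all four groups has:

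1. One SAE definition, reconciling Stop-points with the SAE definition on admissions under 24 hours and elective admissions.
2. One blinded relatedness adjudication, reconciling Safety and hospitalization analysis with Assessment of Causality.
3. One initial reporting path and clock, reconciling the 72-hour rule with the reporting section.

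Word the AE and SAE definitions for any randomised subject. Name the DMC, or another unblinded party outside the site team, to apply the steps that depend on allocation: comparison with the donor sample, supplier contact and the FMT-specific halting triggers. That party should not return the arm to assessors.

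The halting text and the infection text must be reconciled with the blind. This does not call for letting placebo infections pause enrolment, and it prescribes no clinical work-up.

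The cost is a wording amendment, extra reports and relatedness reviews for up to 25 placebo subjects, and one routing step.

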Visit 4: All procedures as in visit 2 will be performed again, including dietary recall, targeted physical exam, and sample collection. All subjects will also get another oral FMT/placebo dose of 5 capsules each depending on their original assignment. All subjects in the study will get this intervention unless (a) they refuse the intervention (b) have undergone a liver transplant or have died/discharged to hospice (c) developed an infection or an SAE that was adjudicated to be related to FMT in the interim or (d) are currently undergoing antibiotic therapy for an infection that is not related to FMT.

For those who are infected due to an FMT-unrelated infection, we will approach the patients 2 days after the completion of the assigned antibiotic course. For those initiated on SBP (Spontaneous Bacterial Peritonitis) prophylaxis, we will provide the intervention after the initial SBP episode is treated. This may require delaying the intervention from day 30 to up to day 45 but this will still be counted as the second FMT.

All other subjects will be given the intervention and the blind will still be maintained. The brain function tests and QOL will be performed again. Groups 1 and 2 will get active FMT and groups 3 and 4 will get placebo FMT. No enemas will be given. The subjects will then be sent home.

Follow-up visits every month: The subjects will be followed monthly in person, or by phone or videoconference at Months 3, 4, 5 to evaluate dietary and medication changes and for safety analysis (hospitalizations, AEs or SAEs), targeted physical exam and for collection of samples at each study clinic visit. Mail-in kits for collection of stool, and urine will be provided along with instructions for use if visit is performed remotely. We will also perform the cognitive tests and QOL assessment at one month post-second intervention and at 6 months. We will continue to follow every patient for 6 months regardless of whether they developed an SAE or hospitalization in between. Only reasons not to follow them up for 6 months would be death, liver transplantation or patient withdrawal of consent.

End-of-Study visit: Per FDA mandates for FMT studies, we will see the patients at six months and we will evaluate AEs, interim hospitalizations, dietary recall, and perform targeted physical exam, QOL and brain function studies, and collect serum, and stool again. At this point the participation of the patient will end.

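### A study-level safety trigger automatically suspends enrollment only; the protocol does not say whether doses still due in subjects already enrolled are held

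*Combined protocol and SAP*

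**What the plan says.** Under Overall Study Halting Rules, the automatic consequence of a listed finding is: "Specific safety findings will result in temporarily suspending enrollment until a safety review is convened". Dosing is dealt with separately in the same section. Later review of serious, unexpected and related AEs "may also result in suspension of further trial interventions/administration of FMT at a site". A standing power is then stated: "The FDA and PI retain the authority to suspend additional enrollment and study interventions/administration of FMT for the entire study, as applicable". On sequence, the section says "The PI and the adjudication panel will make the initial decision" and "The subsequent safety review by the IRB and FDA will then decide if the study can resume". Its sentence on telling the FDA within 72 hours refers to a halt of the study without saying whether dosing is part of it.

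The Visit 4 text says "All subjects in the study will get this intervention unless" one of four exceptions applies: refusal; transplant, death or hospice; the subject's own infection or FMT-related SAE; or current antibiotics for an unrelated infection. It then allows for unrelated infection and SBP prophylaxis: "This may require delaying the intervention from day 30 to up to day 45 but this will still be counted as the second FMT". It goes on: "All other subjects will be given the intervention and the blind will still be maintained". The Visit 2 text has no instruction to hold product during a study-level review.

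Two other provisions can hold product. The Individual study halting rules act on the affected subject. The section on investigating an infection related to FMT requires quarantine of donor material when transmission is suspected.

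**The concern.** A safety pause is meant to limit exposure to a product under review. Enrollment is only one route to exposure here. Subjects are randomized at Visit 1, dosed at Visit 2 (the same day, or up to 8 days later) and dosed again at about day 30. Whenever a trigger fires, some subjects who are not themselves affected will have a first or second dose due. On the express wording they could receive it while, for example, a death related to FMT is being reviewed, unless someone separately decides to hold it.

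The enrollment pause is also worded to last until the review convenes, not until it reaches a decision. In a trial whose primary aim is safety, these points should not be left to interpretation on the day.

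**Working it through.** The plan gives no figure on this point, so there is none to reproduce. The check has two parts.

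**Text, side by side**

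- *Does enrollment include dosing?* No. The standing-power sentence lists enrollment and administration of FMT as two separate things.
- *Is a dosing suspension ever automatic at study level?* No. One mention is a possible result of later review; the other is an authority that the FDA and PI keep. The Safety and hospitalization analysis section sends events voted FMT-related to the stopping rules, which leads back to the same text.
- *Do the visit instructions fill the gap?* No. All four Visit 4 exceptions concern the individual subject, and Visit 2 is silent.
- *Does quarantine fill it?* In part. Of the six listed triggers, two concern transmitted infection. The other four (related death, serious unexpected related AE, new medical or immune-mediated conditions, clusters of similar severe AEs) reach quarantine only if transmission of an infection is the suspected cause. The Rationale describes use of all available donors in the supplier's pool, and each active recipient stays with one donor, so quarantining one donor leaves the others' product available. The risk-minimisation text instead speaks of one donor for all capsules; if that were the practice, quarantine would reach all active capsules and only the non-infection gap would remain.

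**Scale**

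Inputs from the protocol: dose 2 at day 30; four equal groups, two of them with active oral product at day 30 and three with at least one active product at Visit 2. Assumed, because the documents do not say: uniform accrual *a* of 2, 4 or 6 subjects per month, a month of 30.4 days, and review length *L*.

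Second doses falling due during a review of *L* days (*L* ≤ 30) = *a* × *L* / 30.4. Example: 4 × 14 / 30.4 = 1.84.

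| Review length | 2/month | 4/month | 6/month | Active (half) |
|---|---|---|---|---|
| 7 days | 0.46 | 0.92 | 1.38 | 0.23 to 0.69 |
| 14 days | 0.92 | 1.84 | 2.76 | 0.46 to 1.38 |
| 30 days | 1.97 | 3.95 | 5.92 | 0.99 to 2.96 |

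Subject-level holds would lower these counts; faster accrual would raise them. Accrual of 100 subjects in 12 months is 8.3 per month, which gives 8.3 × 30 / 30.4 = 8.2 second doses in 30 days, about 4.1 of them active.

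Subjects awaiting Visit 2 = *a* × gap / 30.4. At the nominal 3-day gap this is 0.20, 0.39 or 0.59; at 8 days it is 0.53, 1.05 or 1.58; with Visits 1 and 2 combined it is 0. Three quarters of them would receive at least one active product.

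**What a full hold would do to the day-45 limit**

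If every Visit 4 fell exactly on day 30, a subject at day *d* when the hold starts would pass day 45 if *d* + *L* > 45, so the number is *a* × max(0, *L* − 15) / 30.4. That is 0 for *L* ≤ 15, and 0.99, 1.97 or 2.96 for *L* = 30.

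The visit windows break the zero. Visit 3 at 10±5 days followed by Visit 4 at 15±3 days allows day 10 + 5 + 15 + 3 = 33, and 33 + 15 = 48. A subject already delayed to day 40 passes day 45 after 6 days (40 + 6 = 46). Short holds can therefore also push some doses past the limit.

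**The case against.** The strongest answer is that the section, read as a whole, describes a study halt. It is headed as halting rules, refers to the study being halted, and makes resumption depend on an IRB and FDA decision. The PI is involved at once and has the power to stop dosing. All treatment visits take place at one VA center with one investigational pharmacy, so a hold would be easy to put in place.

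Much of this stands. A reader might infer that the protocol directs staff to keep dosing through a review, or that a dosing halt would contradict Visit 4. The documents support neither. The Visit 4 exceptions already omit most individual halting rules (a MELD rise of 8, liver enzymes at 10 times ULN, a GI change of 3, and hospitalization not adjudicated FMT-related), so the list is not exhaustive and can yield to rules stated elsewhere. The sentence on all other subjects follows the text on infection and SBP delays, and in context separates undelayed subjects from delayed ones. Nor may one say that dosing cannot be stopped: the power is explicit.

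What the objection does not supply is a written rule that a trigger holds product. The halt language never defines its scope, and the only action stated as automatic is confined to enrollment.

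**Conclusion.** The point holds as a gap and an ambiguity in a safety rule, and should be fixed. On a study-level trigger only enrollment is automatically suspended, and by the wording only until a review convenes. Holding doses in other enrolled subjects depends on a separate decision. The gap is mainly the four non-infection triggers and material from donors who are not implicated.

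The size is modest: under the assumed accrual, roughly 0.5 to 1.4 active second doses in a 14-day review and 1 to 3 in a 30-day review, plus a fraction of a subject to about 1.6 subjects awaiting Visit 2. These figures rest on accrual and review lengths that the documents do not give. The reading of the text does not depend on them.

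**What to change.** Amend Overall Study Halting Rules so that any listed trigger holds both enrollment and all pending study product: Visit 2 and Visit 4 doses, active and placebo, in all four groups so that the blind is kept. The hold should last until the review decides that the study may resume, replacing the present end point at which the review convenes. Add a fifth Visit 4 exception, (e), for an open study-level safety review, and a matching line at Visit 2. State that a second dose delayed by the hold may be given late, up to a stated limit, or is otherwise omitted; the present day-45 allowance is written only for unrelated infection and SBP prophylaxis. Leave six-month follow-up unchanged.

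The cost is a wording amendment and a few second doses delayed or missed per trigger. For a 30-day hold, about 1 to 3 on-schedule doses pass day 45 at the assumed accrual. Even a hold of 15 days or less can push out doses scheduled late in the visit window or already delayed, so the limit for late dosing should be set with that in mind.
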